### 3.6.3 OFF PROTOCOL THERAPY AND OFF-STUDY PROCEDURE

Authorized staff must notify Central Registration Office (CRO) when a subject is taken off protocol therapy and when a subject is taken off-study. A Participant Status Updates Form from the web site ([http:// home.ccr.cancer.gov/intra/eligibility/welcome.htm](http://home.ccr.cancer.gov/intra/eligibility/welcome.htm)) main page must be completed and sent via encrypted email to: NCI Central Registration Office [[contact]](mailto:[contact]).

## **4 CONCOMITANT MEDICATIONS/MEASURES**

At screening, all prior anti-cancer therapy and administration of all other concomitant medication in use on the day of enrollment (signature of the ICF) will be recorded. All concomitant medications that the patient has been taking since the time of the last visit, medications the patient started between visits and all new medications will be recorded at each visit until the completion of the final analysis. If a patient discontinues vandetanib before the final analysis, all medications including any medications started within the 60 days after the last dose of vandetanib, will be recorded at the appropriate discontinuation visit and the 60-day follow-up visit.

### **4.1 PROHIBITED MEDICATION**

Patients are not eligible to enter the study if they have taken any of the medication specified in the exclusion criteria

#### **4.1.1 TREATMENT FOR CANCER**

Prior to starting treatment (according to [Section 2.1](#)) and while the patient remains on study treatment, patients must not be given any concurrent cancer therapy, including cytotoxic agents, radiotherapy, biological response modifiers (including cytokines), hormonal therapy (used specifically for cancer treatment), or any other investigational agents.

#### **4.1.2 CYP3A4 INDUCER**

The administration of vandetanib with strong CYP3A4 inducers (those that induce  $\geq 80\%$  decrease in AUC) should be avoided (per Caprelsa package insert), including avasimibe, carbamazepine, phenytoin, rifampin, St. John's wort. A potent CYP3A4 inhibitor has been shown to have little effects on the exposure to vandetanib and therefore, these agents can be co-administered with vandetanib when indicated.

#### **4.1.3 MEDICATIONS KNOWN TO PROLONG QT INTERVAL AND/OR INDUCE TORSADES DE POINTES**

Concomitant use of medications generally accepted as having a risk of causing Torsades de Pointes (see [Appendix 7](#)) are not allowed within the 2 weeks prior to starting treatment or during study (at least 4 weeks prior for levomethadyl). These drugs should also be avoided for at least 4 weeks following discontinuation of study treatment.

#### **4.1.4 RESTRICTED MEDICATIONS**

All medications prohibited in this study as indicated in [Appendix 7](#) must have been withdrawn at least 2 weeks prior to registration, and should be avoided for at least 4 weeks following discontinuation of study treatment.

Co-administration of drugs that in some reports might be associated with Torsades de Pointes but at this time lack substantial evidence of Torsades de Pointes (see [Appendix 7](#)) should be avoided within the 2 weeks prior to registration, and during the study. However, these drugs will be allowed, at the discretion of the Investigator, if considered absolutely necessary. In such cases, the patient must be closely monitored including regular checks of QTcB and electrolytes. The electrolytes should be maintained within the normal range using supplements if necessary.

Warfarin is allowed in therapeutic and low-doses and these patients should be monitored regularly for changes in their International Normalized Ratio, at the discretion of the Investigator.

Appropriate clinical and/or laboratory monitoring is recommended for patients receiving concomitant metformin and vandetanib, and such patients may require a lower dose of metformin. Appropriate clinical and/or laboratory monitoring is recommended for patients receiving concomitant digoxin and vandetanib, and such patients may require a lower dose of digoxin.

#### 4.1.5 COMPLEMENTARY AND ALTERNATIVE THERAPIES

All complementary or alternative therapies including herbal preparations, vitamins, and supplements should be discussed with the PI or an Associate Investigator. All agents will be recorded on the electronic case report forms.

#### 4.2 HTN MANAGEMENT ALGORITHM

See [Appendix 2](#) and [Appendix 4](#) for monitoring and management of hypertension in children and adults.

#### 4.3 MANAGEMENT OF QTc PROLONGATION

See [Section 3.1.2, Treatment Limiting Toxicity](#).

#### 4.4 MANAGEMENT OF SKIN TOXICITY

- Vandetanib must be held when any CTCAE grade 3 or 4 vandetanib-related skin toxicity occurs. For grade 3 or 4 allergic skin reactions, vandetanib should be discontinued. For non-allergic reactions, treatment may be resumed at a lower dose ([Section 3.3](#)) if the toxicity recovers to grade  $\leq 1$  or baseline within 14 days of discontinuing the drug. If the skin toxicity does not resolve to grade  $\leq 1$  or baseline in  $\leq 14$  days, vandetanib should be discontinued. Rashes should be graded as soon as possible according to the CTCAE cutaneous toxicity criteria.
- Agents that can be used to manage skin rashes include mild to moderate strength steroid creams, topical or systemic antibiotics, topical or systemic antihistamines, and occasionally retinoid creams. If a patient develops a skin rash, the following actions are recommended for the management of this toxicity:
  - For a grade  $\geq 2$  vandetanib-related rash, immediate symptomatic treatment with topical creams or systemic anti-histamines should be provided.
  - For grade  $\geq 3$  vandetanib-related rash (non-allergic), vandetanib should be held until recovery to grade  $\leq 1$ . After recovery, vandetanib may be restarted at a reduced dose ([Section 3.3](#)) after discussion with the protocol PI. If the rash does not resolve to grade  $\leq 1$  in  $\leq 14$  days OR the rash is an allergic rash, vandetanib will be discontinued.
  - It is strongly recommended that all patients use sun-protective measures while receiving vandetanib and for 3-4 weeks after discontinuing vandetanib to reduce the risk of developing skin rash or minimize the severity of skin rash.

#### 4.5 MANAGEMENT OF GASTROINTESTINAL TOXICITY

Electrolytes should be closely monitored in the event of persistent vomiting or diarrhea. Vandetanib should be held in patients who develop electrolyte abnormalities from vomiting or diarrhea until the electrolyte abnormalities are corrected because of the risk of QTc prolongation and subsequent arrhythmias.

#### 4.5.1 NAUSEA OR VOMITING

Nausea, vomiting, or both may be controlled with antiemetic therapy. The use of somatostatin or a somatostatin analogue is allowed to control diarrhea. There is a risk that the use of 5HT-3 antagonists may prolong QTc interval; therefore, these agents are prohibited. The dose of vandetanib may be repeated once if emesis occurs within 30 minutes of taking the dose.

#### 4.5.2 VANDETANIB-RELATED DIARRHEA

Diarrhea that occurs after initiation of vandetanib is likely to be treatment-related and should be treated symptomatically to avoid dose modification or interruption. Diarrhea due to vandetanib has been successfully managed in adults with anti-diarrheal agents such as loperamide. No dose modifications will be made for Grade 1 or 2 diarrhea, however, electrolyte supplementation with regular laboratory monitoring should be used when appropriate, to maintain electrolytes within normal limits and prevent an increased risk of QTc prolongation. Any electrolyte imbalance must be promptly corrected since hypokalaemia and hypomagnesaemia are potential risk factors for drug-induced arrhythmia.

If grade 3 diarrhea that cannot be controlled by symptomatic treatments within 48 h or grade 4 diarrhea develops, or diarrhea worsens by one grade level (grade 3 to grade 4) while on vandetanib and is not alleviated by symptomatic treatment within 48 h, vandetanib should be held until diarrhea resolves to grade  $\leq 1$  or baseline. Once the diarrhea resolves, vandetanib may be restarted at a reduced dose ([Section 3.3](#)). Dose reduction should only occur if the investigator believes the diarrhea is related to vandetanib.

## 5 BIOSPECIMEN COLLECTION

### 5.1 CORRELATIVE STUDIES FOR RESEARCH

#### 5.1.1 EVALUATION OF ARCHIVAL TUMOR TISSUE

Archival tumor tissue will be evaluated for SDH expression in consenting patients if tissue is available. Additional Immunohistochemistry (IHC) studies will be performed at the Laboratory of Pathology, CCR, NCI as they become available.

#### 5.1.2 TUMOR TISSUE (OPTIONAL)

Patients who require surgery will be invited to participate in (prior to participation, patient must have consented to this optional analysis as contained in the informed consent document):

#### 5.1.3 ANALYSIS OF TUMOR TISSUE

Patients who agree to allow tumor tissue for research study will have tissue evaluated for SDH expression; immunohistochemistry (IHC) performed at the Laboratory of Pathology, CCR, NCI.

#### 5.1.4 CELL LINE ESTABLISHMENT:

Given the rare nature of tissue available from this patient population, attempts will be made to establish wt-GIST cell lines when surgery or biopsy during the trial are clinically indicated. Gene expression arrays and eventually protein lysate arrays will be created with the aim to identify potential molecular targets for new therapy development. Cell lines will also be used to perform *in vitro* testing of new agents. Informed consent will be required for this purpose, and subjects will be given the option to decline having cell lines established from their samples.

Fresh tumor samples from consenting patients who require clinically indicated surgery or biopsy will be placed immediately into tissue culture medium and transported directly to the Molecular Oncology Section of the Pediatric Oncology Branch.

Samples should be submitted to:

[name]  
[name]  
[name]  
[name]  
[contact]

#### 5.1.5 [F]-FDG-PET/CT SCAN (OPTIONAL)

Patients who are 15 years of age and older will be asked to participate in one additional [F]-FDG PET/CT scan (optional) on day 3 to day 6 after starting treatment with vandetanib. The purpose of this research [F]-FDG PET/CT scan will be to evaluate the utility of [F]-FDG -PET/CT to predict response early in the treatment of wt- GIST.

Patients will be required to have nothing by mouth at least 4 hours prior to the [F]-FDG PET/CT scan. They must arrive in the PET Department with IV access already in place. [F]-FDG will be administered over one minute IV in a dimly lit, quiet prep room. The patient must then remain still in a quiet room with lights dimmed and refrain from talking. Thirty minutes after the initial injection, the patient will be asked to empty their bladder. Forty- to forty-five minutes post-injection, scanning will begin. Patients will be asked to void again at 90 minutes after [F]-FDG injection and then at least every 3-4 hours for the remainder of the day.

Patients will receive radiation from one optional [F]-FDG PET/CT for research purposes on this protocol. The [F]-FDG PET/CT scan will entail the injection of 10mCi dose for all ages and body sizes. In adults, the total additional radiation dose for research purposes will be 1.14 rem, and in children 15 years of age and older, the total additional radiation dose for research purposes will be 1.4 rem.

## 5.2 BLOOD DRAWING LIMITS FOR RESEARCH PURPOSES

The amount of blood that may be drawn from adult patients and volunteers (i.e., those persons 18 years of age or older) for research purposes shall not exceed 10.5 mL/kg or 550 mL, whichever is smaller, over any eight week period. The amount of blood to be drawn from volunteers and the frequency of collection shall be specified in the clinical research protocol, and exceptions to the 10.5 mL/kg or 550 mL limitations shall be approved by the IRB.

For pediatric patients, no more than 5 mL/kg may be drawn for research purposes in a single day, and no more than 9.5 mL/kg may be drawn over any eight-week period.

## 5.3 SAMPLE STORAGE, TRACKING AND DISPOSITION

Samples will be ordered in CRIS and tracked through a Clinical Trial Data Management system. Should a CRIS screen not be available, the CRIS downtime procedures will be followed. Samples will not be sent outside NIH without IRB notification and an executed MTA.

Blood and tissue collected during the course of this study will follow NIH guidelines for the research use of human samples and OHRP Issues to Consider in the Research Use of Stored Data

or Tissues. All samples (blood or tissue) are documented in LabMatrix and tracked by distinct identification labels that include a unique subject identifier and date of specimen collection with computer backup according to established standards for the Central Repository for NCI-Frederick. All cryopreserved samples are tracked for freezer location and storage criteria. All samples are stored in monitored freezers/refrigerators either in the Central Repository for NCI-Frederick or in the investigator's laboratory at specified temperatures with alarm systems in place. The system will contain data that includes, but is not limited to the unique sample identifiers, storage locations and conditions, biologic study results, clinical information, and corresponding records of all derivatives generated from samples/tissues collected on this protocol. The system will employ mechanisms for restricting users to viewing only the level of data appropriate for each individual user, will provide the capability to audit any data modification, and will be maintained and backed up according to established standards.

At the termination of this protocol, if additional studies are to be performed on any human subject samples retaining patient identifiers or codes obtained during the conduct of this trial, a Request to Conduct Research for Stored Human Samples Specimens, or Data Collected in a Terminated NCI-IRB Protocol will be submitted. Otherwise, specimens will be disposed of in accordance with the environmental protection laws, regulations and guidelines of the Federal Government and the State of Maryland. Any new uses of human subject samples collected during the course of this trial must be reviewed and approved by the NCI IRB. Any loss or unintentional destruction of the samples will be reported to the IRB.

## **6 DATA COLLECTION AND EVALUATION**

### **6.1 DATA COLLECTION**

The PI will be responsible for overseeing entry of data into an in-house password protected electronic system (C3D) and ensuring data accuracy, consistency and timeliness. The principal investigator, associate investigators/research nurses and/or a contracted data manager will assist with the data management efforts. All data obtained during the conduct of the protocol will be kept in secure network drives or in approved alternative sites that comply with NIH security standards. Primary and final analyzed data will have identifiers so that research data can be attributed to an individual human subject participant.

All adverse events, including clinically significant abnormal findings on laboratory evaluations, regardless of severity, will be followed until return to baseline or stabilization of event.

An abnormal laboratory value will be recorded in the database as an AE **only** if the laboratory abnormality is characterized by any of the following:

- Results in discontinuation from the study
- Is associated with clinical signs or symptoms
- Requires treatment or any other therapeutic intervention
- Is associated with death or another serious adverse event, including hospitalization.
- Is judged by the Investigator to be of significant clinical impact

- If any abnormal laboratory result is considered clinically significant, the investigator will provide details about the action taken with respect to the test drug and about the patient's outcome.

**End of study procedures:** Data will be stored according to HHS, FDA regulations, and NIH Intramural Records Retention Schedule as applicable.

**Loss or destruction of data:** Should we become aware that a major breach in our plan to protect subject confidentiality and trial data has occurred, the IRB will be notified.

Clinical data will be shared with AstraZeneca.

Questionnaire (PROMIS and Distress Thermometer) data will be entered into an SPSS (version 12.0.1), SPSS, Chicago, IL) database by a research assistant. Personal identifiers will not be used when collecting and storing data. Questionnaire data will be linked with clinical data through the use of the unique subject identification number. Files will be stored in password-protected folders and accessible only to the personnel in the POB NCI Psychosocial Support and Research Program.

## **6.2 DATA SHARING PLANS**

### **6.2.1 GENOMIC DATA SHARING PLAN**

Unlinked genomic data will be deposited in public genomic databases such as dbGaP in compliance with the NIH Genomic Data Sharing Policy.

## **6.3 RESPONSE CRITERIA**

For the purposes of this study, participants must have measurable disease as defined in RECIST (v1.1) as the presence of at least one lesion that can be accurately measured in at least one dimension with longest diameter of at least 20 mm using conventional techniques or at least 10 mm with spiral CT scan. Patients should be re-evaluated for response every 3 cycles x 4 (prior to cycle 4, 7, 10, 13) and then every 6 cycles. In addition to a baseline scan, confirmatory scans should also be obtained at least 4 weeks following initial documentation of objective response.

Response and progression will be evaluated in this study using the new international criteria proposed by the revised Response Evaluation Criteria in Solid Tumors (RECIST) guideline (version 1.1) (44) Changes in the largest diameter (unidimensional measurement) of the tumor lesions and the shortest diameter in the case of malignant lymph nodes are used in the RECIST criteria.

### **6.3.1 DEFINITIONS**

Evaluable for toxicity: All patients will be evaluable for toxicity from the time of their first treatment with Vandetanib.

Evaluable for objective response: Only those patients who have measurable disease present at baseline, have received at least one cycle of therapy, and have had their disease re-evaluated will be considered evaluable for response. These patients will have their response classified according to the definitions stated below. (Note: Patients who exhibit objective disease progression prior to the end of cycle 1 will also be considered evaluable.)

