### 3.3 DOSE MODIFICATIONS

#### 3.3.1 GENERAL GUIDANCE

Vandetanib should be held for any treatment-limiting toxicity (see Section 3.1.2). For treatment limiting toxicities that include a duration in the definition, such as a neutrophil count below 1,000/ $\mu$ L (grade 3) on 2 consecutive measurements drawn at least 72 hours, the drug will be held after the toxicity reaches the grade defined in treatment limiting (e.g., after the second ANC <1,000/ $\mu$ L).

If vandetanib-related treatment-limiting toxicity resolves to grade  $\leq$ 1 or baseline in  $\leq$ 6 consecutive weeks of drug free period, vandetanib may be restarted at a reduced dose.

If the vandetanib-related treatment-limiting toxicity does not resolve to grade  $\leq 1$  or baseline in  $\leq 6$  consecutive weeks of a drug free period the patient should discontinue protocol therapy and be monitored until the toxicity resolves.

The cycle duration remains 28 consecutive days in patients who have dose interruptions.

If a patient happens to miss 6 weeks of dosing for non-toxic events, if monitoring is initiated as described in Section 3.5.1, the patient may initiate re-dosing.

Refer to Section 4 Concomitant Medications/Measures for management of specific toxicities.

Refer to Section 3.1.1 for intra patient dose escalations.

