### 3.5.3 POST TREATMENT FOLLOW UP

#### 3.5.3.1 Off-Treatment Evaluation

Patients who have been taken off treatment for any of the criteria in [Section 3.6.1](#), will be monitored until resolution of toxicity, as clinically indicated, and efforts will be made to return to NIH at least once for Off-Treatment evaluation (at least 60 days after the last dose of vandetanib) for:

- Physical Examination with vital signs
- Laboratory Evaluation: CBC and differential, chemistry and liver function tests
- Toxicity assessment

Patients unable to return to NIH will be contacted by a member of the research team approximately 60 days after the last dose of investigational drug for an evaluation of toxicity.

Patients or the local medical provider will be contacted at least annually to obtain current status on patients who have completed the off treatment evaluation, until one of the off study criteria ([Section 3.6.2](#)) are met.

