### 3.6.1 CRITERIA FOR REMOVAL FROM PROTOCOL THERAPY

Subjects will be removed from study therapy and followed until off-study criteria are met for any one of the following:

- Unacceptable toxicity (treatment limiting toxicity after two dose reductions, or treatment-limiting toxicity does not resolve to grade  $\leq$ 1 or baseline in  $\leq$  6 weeks of a drug free period). Patients who are removed from therapy for unacceptable toxicity will continue to undergo disease evaluations as per [Appendix 9](#) until they develop progressive disease.

- Concurrent use of agents that prolong the QTc: Vandetanib use must be discontinued if one of the QTc prolonging agents in Group 1 of [Appendix 7](#) is started.
- Progressive disease; clinical or radiographic evidence of progressive disease will discontinue vandetanib (see [Section 6.3](#)). If possible, tumor progression should be documented radiographically.
- Participant requests to be withdrawn from active therapy
- Positive pregnancy test
- Investigator discretion, which may include
  - The development of a concurrent serious medical condition that might preclude or contraindicate the further administration of vandetanib.
  - It is deemed in the best interest of the patient, and the reasons for discontinuation of vandetanib should be noted in the patient's medical record.
  - Serious protocol violation, such as non-compliance, as determined by the Principal Investigator.
- Death

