#### **For Patients with Measurable Disease (i.e., Target Disease)**

Target Lesions	Non-Target Lesions	New Lesions	Overall Response	Best Overall Response when Confirmation is Required*
CR	CR	No	CR	$\geq 4$ wks. Confirmation**
CR	Non-CR/Non-PD	No	PR	$\geq 4$ wks. Confirmation**
CR	Not evaluated	No	PR	
PR	Non-CR/Non-PD/not evaluated	No	PR	
SD	Non-CR/Non-PD/not evaluated	No	SD	Documented at least once $\geq 4$ wks. from baseline**
PD	Any	Yes or No	PD	no prior SD, PR or CR

Any	PD***	Yes or No	PD	
Any	Any	Yes	PD	

* See RECIST 1.1 manuscript for further details on what is evidence of a new lesion.
 
** Only for non-randomized trials with response as primary endpoint.
 
*** In exceptional circumstances, unequivocal progression in non-target lesions may be accepted as disease progression.
 
Note: Patients with a global deterioration of health status requiring discontinuation of treatment without objective evidence of disease progression at that time should be reported as “symptomatic deterioration.” Every effort should be made to document the objective progression even after discontinuation of treatment.
				

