## 20 APPENDIX 9: REQUIRED STUDY EVALUATIONS

Clinical and laboratory tests to determine eligibility must be performed within 7 days prior to enrollment unless otherwise indicated. Laboratory values used to assess eligibility must be no older than 7 days at the start of therapy. Laboratory tests need not be repeated if therapy starts within 7 days of obtaining labs for eligibility. For further details see [section 2.2](#).

STUDIES TO BE OBTAINED 	Screening	Baseline	During Cycle 1	Prior To Subsequent Cycles	End of Therapy 
PT/PTT	X				
Lower leg scanogram 		X			
History, physical exam, vital signs (HR, BP, Temp) CBC, differential, platelets Chemistries: [Acute Care Panel (sodium, potassium, chloride, CO 2 , creatinine, glucose, BUN), Mineral Panel (calcium, magnesium, phosphorus, albumin) Hepatic Panel (alk phos, ALT/AST, Total bilirubin, (if T Bili is elevated, draw Direct bilirubin) total protein, uric acid, LDH.	X		Day 14	Prior to cycles 2, 3, 4, and then after every 3 cycles prior to cycle 7, 10, 13, etc)	X
Urinalysis		X	-	Prior to cycles 2, 3, 4, and then after every 3 cycles prior to cycle 7, 10, 13, etc)	X
Thyroid function (TSH; T4 if TSH abnormal)		X			
EKG	X				
Height, weight, BSA, Performance Status β -HCG pregnancy test: (if applicable)  Disease evaluation: CT chest/abdomen/pelvis, MRI abdomen/pelvis Unilateral knee MRI 	X			Prior to cycle 4, 7, 10, 13, and then after every 6 cycles (prior to cycle 19, 25, 31, etc)	X
FDG-PET scan 	X		Day 3 to 6 	Prior to cycle 4	
QOL: PROMIS and Distress Thermometer		X		Prior to cycle 4	X
Patient diary: reactions/symptoms and concomitant meds 	-	X	Daily	Daily until prior to cycle 13	-
Study calendar 	-		-	From cycle 13 on	X
NIH Advance Directives Form 		X			

With exception of the optional FDG-PET scan, study evaluations for cycles 1 through 4 may be performed within +/- 3 days of the scheduled date.

Study evaluations for cycles  $\geq 5$  may be obtained within +/- 7 days of the scheduled date.

Lower extremity scanogram in all participants less than 18 years old. Patients with fused growth plates will not undergo additional evaluations. Patients with open growth plate(s) will also undergo follow up scanogram only if clinically indicated.

Required in females of childbearing potential.

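### Section 6.3.1 leaves some treated patients out of the response rate and nothing counts them as non-responders: report an all-treated rate beside it

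*Combined protocol and SAP*

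**What the plan says.** **Who counts.** Section 6.3.1 limits response evaluation to "Only those patients who have measurable disease present at baseline, have received at least one cycle of therapy, and have had their disease re-evaluated". Its note adds patients with objective progression before the end of cycle 1. Section 8.1 defines the numerator (CR and PR) but no rule for treated patients who were not assessed. Section 8.2 puts PFS and OS on all enrolled patients; that wording does not reach ORR.

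**How many.** The précis and 8.1 ask for 9 evaluable patients in stage 1 and then 24 enrolled. Section 8.3 asks for 24 evaluable and sets a ceiling of 27 to leave room for inevaluable patients, described in a parenthetical as those who withdraw before reaching progression or toxicity. It also records that nine patients had enrolled when accrual closed.

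**Imaging after stopping.**
- Appendix 9 lists "Disease evaluation: CT chest/abdomen/pelvis, MRI abdomen/pelvis" and marks it at End of Therapy, whatever the reason for stopping.
- Section 3.6.1: "Patients who are removed from therapy for unacceptable toxicity will continue to undergo disease evaluations" until progression. For progressive disease: "If possible, tumor progression should be documented radiographically".
- The note to the response table in 6.3.4.3: "Every effort should be made to document the objective progression even after discontinuation of treatment".
- Section 3.5.3.1: "efforts will be made to return to NIH at least once for Off-Treatment evaluation". Its list covers examination, laboratory tests and toxicity, with no imaging.

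**Stopping in cycle 1.** Section 3.3.1: "The cycle duration remains 28 consecutive days in patients who have dose interruptions". Section 4.4: "For grade 3 or 4 allergic skin reactions, vandetanib should be discontinued".

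**The concern.** A patient who dies, refuses or fails clinically before any scan is, in nearly every case, not a responder. Removing that patient shrinks the denominator and leaves the numerator alone, so whenever there is at least one response the ORR will usually be overstated. The reason for exclusion is tied to the outcome, so this is not neutral missing data.

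The second issue is the stage 1 count. The rule in 8.1 is written for nine evaluable patients, and exactly nine were enrolled. One exclusion under 6.3.1 leaves eight, and with accrual closed there is no replacement.

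**Working it through.** **1. The plan's own figure.** Inputs from 8.1: null rate 5%, target rate 25%, stop if 0 of 9 respond. Probability of early termination under the null = (1 − 0.05)^9 = 0.6302, which matches the stated 63%. The design arithmetic is not in question.

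**2. Who falls outside 6.3.1.** Measurable disease is an inclusion criterion (2.1.1.3), so only the other two conditions can exclude an eligible patient.

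| Case | What narrows it | What remains |
|---|---|---|
| (a) Under one cycle, no objective progression | Section 3.3.1 keeps the cycle clock running through interruptions. One route to removal for toxicity in 3.6.1 is non-resolution over 6 drug-free weeks (42 days, longer than the 28-day cycle); the other needs two prior dose reductions. Most toxicity removals therefore fall after cycle 1. | Discontinuation in cycle 1 under 4.4, or at the patient's request (3.6.1). A later scan cannot supply the missing cycle. |
| (b) Never re-evaluated | End-of-therapy evaluation in Appendix 9; continued scans after a toxicity stop in 3.6.1; slow-growing tumours (1.2.1), so very early death or clinical failure should be uncommon. | Death, refusal or clinical failure before any scan. The first scheduled restaging is before cycle 4, that is after 3 × 28 = 84 days. The other provisions speak of efforts, or of what is possible. |

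Both cases are small and neither is empty.

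**3. Effect on the reported ORR.** Let n be the number of the nine who meet 6.3.1. ORR = x/n. The exact (Clopper-Pearson) 95% limits for x ≥ 1 are the 0.025 quantile of Beta(x, n − x + 1) and the 0.975 quantile of Beta(x + 1, n − x). For x = 0 the upper limit is 1 − 0.025^(1/n).

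| n | One response: ORR (95% limits) | Zero responses: ORR, upper limit |
|---|---|---|
| 9 | 1/9 = 11.1% (0.3 to 48.2) | 0%, 33.6% |
| 8 | 1/8 = 12.5% (0.3 to 52.7) | 0%, 36.9% |
| 7 | 1/7 = 14.3% (0.4 to 57.9) | 0%, 41.0% |

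With one response, the shift from n = 9 is 12.5 − 11.1 = 1.4 points for one exclusion and 14.3 − 11.1 = 3.2 points for two.

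**4. Effect on stage 1.** Chance of zero responses if the true rate is 25%:

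- n = 9: 0.75^9 = 0.0751, or 7.5%
- n = 8: 0.75^8 = 0.1001, or 10.0%
- n = 7: 0.75^7 = 0.1335, or 13.3%

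At a true 5%, the same chance is 0.95^8 = 0.663 for n = 8 and 0.95^7 = 0.698 for n = 7, so the 63% in 8.1 describes nine evaluable patients only.

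**The case against.** The best defence is that 6.3.1 is explicit and prespecified, keeps early objective progressors in, and is the only formal definition of the response set. The imaging provisions and the cycle rule leave few patients outside it. Section 8.1 plans no confidence interval for ORR (the 95% intervals in 8.2 are for PFS and OS), so the change in the limits concerns a quantity that this review proposes to add. All of this stands, and it is why 6.3.1 should remain the prespecified analysis. It does not supply the missing rule: a patient outside the set is still silently dropped.

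A reader might infer that 8.1 and 8.3 set rival denominators. They do not. Stage 1 is worded as evaluable, and 8.3 says evaluable and explains the ceiling of 27, so the 24 in 8.1 is best read as evaluable too. The parenthetical in 8.3 explains spare places and is not a definition, although it suggests that a patient who stops for toxicity is evaluable when 6.3.1 can exclude that patient. This is a wording clean-up.

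A reader might also infer that the error rates of the 24-patient design are compromised. That stage can no longer occur, and the documents give no exclusion rate from which to compute an effect.

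Finally, a reader might argue that the rule could equally hide a true response in a patient treated for under one cycle. That is remote: 1.2.1 describes slow-growing tumours, and 1.2.2 reports that shrinkage in medullary thyroid carcinoma came gradually over several cycles.

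**Conclusion.** The point holds and is minor. The 6.3.1 rule can remove treated patients from the primary ORR, and nothing in the documents returns them as non-responders. If there is one response, one or two exclusions raise the ORR from 11.1% to 12.5% or 14.3%. If there is none, the ORR is 0% on any denominator and only the upper limit moves. With fewer than nine evaluable patients, the stage 1 properties in 8.1 no longer describe the data.

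It would go too far to conclude that this trial's ORR is inflated. The documents do not report how many of the nine meet 6.3.1 or how many responded, so the actual effect may be nil. The denominators 8 and 7 are illustrations, and the direction of bias assumes that patients lost early are non-responders.

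**What to change.** Keep the 6.3.1 set as the prespecified analysis. Beside it, labelled as added after accrual closed, report:

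> ORR with an exact 95% confidence interval on all eligible patients who received at least one dose of vandetanib. A patient with no post-baseline disease assessment, for any reason, is a non-responder. Only responses that meet section 6.3.4 and are documented before any new anticancer therapy are counted.

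The cut-off is needed because 4.1.1 bars other cancer therapy only before and during study treatment, while best response in 6.3.4.3 runs until progression. Without it, a response to a later drug could be credited to vandetanib.

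Also:
- List each patient outside the 6.3.1 set with the reason.
- Say evaluable, with a reference to 6.3.1, throughout the précis, 8.1 and 8.3, and make the parenthetical in 8.3 match 6.3.1.
- If fewer than nine patients meet 6.3.1, state that the stage 1 properties in 8.1 do not apply to that set.

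The cost is some rewording, one extra table, and an all-treated ORR that may be slightly lower. Because outcomes may already be known, the added analysis should sit beside the prespecified one and not replace it.
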